**Randomized Controlled Trial of Talc Instillation In Addition To Daily Drainage
Through a Tunneled Pleural Catheter to Improve Rates of Outpatient
Pleurodesis in Patients with Malignant Pleural Effusion – The ASAP II Trial**

Participating Sites:

Duke University Medical Center

Durham VA Medical Center

NCT04792970

Version Date: 01/01/2021

Purpose of the Study

To assess the efficacy of talc instilled via tunneled pleural catheter combined with daily drainage to induce accelerated pleurodesis in patients with malignant pleural effusion. *Our hypothesis is that the combination of talc instillation with daily drainage will increase rates of pleurodesis compared with daily drainage alone.*

Background and Significance

Tunneled Pleural Catheters (TPC's) are an increasingly utilized for the management of malignant pleural effusions (MPEs). TPCs provide rapid relief of dyspnea and improvement in quality-of-life in patients with MPEs.^{1,2} Spontaneous pleurodesis may occur through repetitive drainage of the pleural space, however the rates and timing of this event are variable and have been reported to be between 16% and 65%.^{1,3,4} Earlier pleurodesis leads to lower supply costs and reduced risk of long term complications such as infection, pain or mechanical failure.^{5,6} This is especially important as malignant pleural effusion is associated with a generally poor prognosis and if given limited life expectancy, minimizing medical interference and hospitalized days is paramount.^{7,8}

Recent advances in the field of malignant pleural effusion management have prioritized these patient centered goals of maximizing quality of life improvements while minimizing time in the hospital. Recent research by our own group has shown a 20% improvement in the percentage of patients having their TPC removed by 12 weeks with high volume daily drainage of pleural effusions at home.⁹ Parallel research has demonstrated that the addition of talc through a TPC achieves a similar 20% improvement in pleurodesis within the first 5 weeks.¹⁰ Somewhat surprisingly, the rates of pleurodesis were nearly identical between the 2 studies at 48% and 43% respectively^{9,10}. Notably, patients in the talc study drained their effusions using an every other day or symptom guided strategy rather than daily drainage.

We hypothesize that combining both strategies (daily drainage with the addition of talc sclerosant) will lead to both earlier, and higher incidence of pleurodesis in the majority of treated patients. We believe that this can be achieved on an outpatient basis without additional interactions with the healthcare system.

Design and Procedures

To assess if the addition of talc sclerosant to daily outpatient drainage compared with daily drainage alone leads to more rapid pleurodesis.

Study Type: Non-blinded prospective randomized two-arm cohort

Primary Endpoint: Proportion of cohort able to have TPC removed at 30 days post talc-administration (day of randomization will be defined as study day 1)

Secondary Endpoints: Quality-of-Life Assessment, dyspnea assessment, adverse events

Schedule of Events:

	Screening (up to 14 days prior to baseline visit)	Baseline (Day 0)	30 day follow-up visit	60 day follow-up visit
Tunnel Pleural Catheter insertion (SOC*)	X			
Chest x-ray (SOC)	X		X	X
Physical Exam (SOC)	X	X	X	X
Randomization		X		
Talc instillation (if randomized to Talc Arm) (SOC)		X		
Vital sign monitoring for 2 hours post Talc instillation (if randomized to Talc Arm) (SOC)		X		
SOB VAS questionnaire		X	X	X
SF-36 questionnaire		X	X	X
Daily drainage diary review		X	X	X
AE review		X	X	X

*Standard of Care (SOC) procedures

Enrollment

Patients will undergo TPC insertion for malignant pleural effusion as per usual clinical indications and protocols in either the inpatient or outpatient setting. Patients will be eligible for study enrollment anytime between catheter insertion and initial clinical follow-up at a maximum of 14 days following TPC insertion. Patients will be instructed to drain that catheter daily until initial follow-up. At this 7-14 day follow-up appointment for suture removal patients will be asked to drain the morning of the clinic visit and a chest x-ray (CXR) will be performed prior to the clinic visit. The catheter may be drained at the time of the clinic visit if not done within 8 hours of the visit. Patients who meet radiographic criteria for inclusion (see inclusion/exclusion criteria below) may proceed with randomization via central computer generated randomization table. Those who do not meet radiographic criteria will be considered screen

failures and withdrawn from the study. At the time of randomization, patients will be given baseline symptom surveys, a drainage diary, and talc instillation or daily drainage alone based on study arm.

Tunneled Pleural Catheter Placement

All patients will have undergone placement of a tunneled pleural catheter prior to consideration for trial enrollment. These are placed utilizing a standard sterile technique under ultrasound guidance. Local Anesthetic will be utilized for placement, which will be performed under sterile conditions on an inpatient or outpatient basis at the discretion of the patient's treatment team. Moderate sedation may be utilized during placement at the treating physicians discretion.

Sclerosant Infusion Procedure

All patients randomized to the Talc arm will receive a slurry composed of 10cc of 1% lidocaine and 4g of graded talc suspended in 50cc of 0.9% saline infused through the pleural catheter. The line will be flushed with a further 10cc of 0.9% normal saline and then de-accessed and dressed in the usual fashion. Control arm patients will not receive any additional therapy. The patients receiving talc will be monitored on-site for 2 hours for the development of dyspnea, followed by drainage of the catheter. Vitals signs will be monitored for stability prior to discharge home. All patients will be instructed to perform drainage daily for the duration of the trial or until catheter removal.

Drainage

All patients will receive drainage bottles after placement and throughout the study to ensure maximum drainage. Patients and their care givers will be instructed on sterile technique for drainage utilizing the tunneled pleural catheters.

Follow up

Study subjects will return for clinic visits at day 30 and 90 after randomization, or a final visit at the time of catheter removal (Figure 1). Review of drainage logs, repeat CXR, SOB VAS and questionnaire, and quality of life measures will be collected at these timepoints. Day 30 and 90 follow up appointments are standard of care for follow up of tunneled pleural catheter management. Additional visits will occur as clinically indicated.

Criteria for Pleurodesis

Pleurodesis is defined as three consecutive drainage attempts with 50cc or less or less than 200cc in 1 week. Patients will be instructed to contact their treatment team who will obtain a CXR to evaluate for resolution of effusion. A CXR showing effusion \leq the size of the effusion at randomization will be considered to be successful pleurodesis. Chest x-ray imaging showing an effusion larger than what was present at randomization (radiographic score 2-5) will be investigated for dysfunction of the pleural catheter. Thoracic ultrasound will be performed at the time of removal of each catheter to assess for presence and size of residual pleural fluid, pleural septations, and for the presence or absence of lung sliding (appendix 1).

Management of Dysfunctional Catheters

Obstructed catheters will be investigated per ASAP I protocol by instillation of 2mg TPA in 8ml sterile water and allowed to dwell for 20 minutes followed by drainage. If the output returns to $>200cc$

after fibrinolytic infusion then patient will return to study protocol. If fibrinolytic fails to produce immediate drainage and the patient does not have shortness of breath the catheter will be removed and the patient will be considered to have undergone partial response. Patients with continued shortness of breath will be managed at the discretion of the treating physician and will be considered catheter failures.

Outcome Measures

Primary Outcome: Percentage of cohort undergoing accelerated pleurodesis. Patients able to have their TPC removed at 30 days post-talc instillation will be considered to have achieved the primary endpoint. Pleurodesis is defined as three consecutive drainage attempts with 50cc or less or less than 200cc in 7 days and lack of respiratory symptoms of cough or shortness of breath previously attributed to pleural effusion. Patients will be considered to have experienced complete (CR) or partial response (PR) depending on chest x-ray (CXR) scoring criteria. Patients who experience pleurodesis later than 30 days from randomization will be considered to have a delayed CR or PR using the same CXR scoring criteria.

Chest X-ray scoring (see appendix 1): Chest x-ray scoring will be performed by a blinded pulmonologist viewing images identified with study code on a CD supplied by the treating physician. Patients with CR will have a CXR score of 0-1, and PR ≥ 2 .

Secondary Outcomes: Dyspnea and Quality-of-Life Measurements. Baseline Dyspnea measurements will be performed by Visual Analog Scale (VAS), a validated measure of dyspnea in pleural disease. Quality-of-Life measurements will be performed using the short form 36 (SF-36) which is a validated survey-based tool that measures 8 aspects of physical and mental well being. Both of these survey tools will be administered at enrollment, 30, and 90 days after randomization, or at the time of catheter removal if prior to the 30 day or 90 day clinical follow-up. Because patients will be randomized after catheter insertion and drainage for 7 to 14 days, we anticipate dyspnea and QOL to be somewhat optimized as related to interactions from pleural fluid at randomization. The assessments will be examining stability of symptom control over the course of study enrollment.

Adverse Events

Anticipated adverse events include pain with drainage, catheter dislodgement, catheter malplacement, insertion site cellulitis, and empyema. Catheter obstruction due to fibrin will be considered catheter failure, but not an adverse event. There is an extremely small chance of a patient developing local anesthetic systemic toxicity from the instillation of lidocaine mixed with the talc slurry. Intralipid, used to treat this serious complication will be stored in the outpatient procedure suite pyxis.

Selection of Subjects and Data Collection

Diagnosis and Inclusion Criteria:

Subjects must meet all of the following:

1. Male or female, at least 18 years of age, inclusive.
2. Subject has a symptomatic MPE requiring intervention. For an effusion to be defined as malignant, at least one of the following must be true:
 - a. There is histocytological confirmation of pleural malignancy
 - b. The effusion is an exudate (per Light's criteria) in the context of histocytologically proven malignancy elsewhere, with no other clear cause

for fluid identified.

3. Subject has a history of at least 1 ipsilateral pleural effusion causing dyspnea that responded to thoracentesis where the lung expanded and the dyspnea was improved.
4. Subject is willing and able to provide written informed consent.
5. Subject is willing and able to meet all study requirements, including follow-up visits and receiving study-related telephone calls.
6. Subject has sufficient pleural fluid to allow safe insertion of an IPC.
7. Subject has negative pregnancy test if appropriate.
8. Subject or caregiver is able to perform home drainage of the pleural effusion (a caregiver can be a friend, family member, or paid healthcare professional).

Exclusion Criteria:

Potential study subjects will be excluded if 1 or more of the following exclusion criteria is present:

1. Subject has significant trapped lung, or a proximal bronchial obstruction which is likely to lead to trapped lung. For a subject to be eligible for this study, two separate study center clinicians must agree that there is no significant trapped lung on the same CXR using visual estimation (reference guide). The CXR used to make this decision must have been performed ≤ 30 days preceding the consent form being signed, and must have been performed preferably on the same day, but no more than 7 calendar days after tunneled pleural catheter insertion.

Significant trapped lung is deemed present if any 1 of the following criteria is met:

- a) A CXR shows hydropneumothorax other than small (< 1 cm between chest wall and pleural line) apical pneumothoraces.
- b) A CXR shows $\geq 20\%$ of the affected hemithorax to be free of the expected lung parenchymal markings and there is no suggestion of pleural fluid.
- c) A CXR shows $\geq 20\%$ of the affected hemithorax to be occupied with pleural fluid AFTER a pleural aspiration which resulted in symptoms suggestive of trapped lung (e.g., chest pain or cough).
2. Subject has a Karnofsky score < 50 , or a World Health Organization (WHO)/Eastern Cooperative Oncology Group (ECOG) performance status ≥ 3 . Subjects who have a performance status of 3 may be considered for the study if the removal of their fluid would likely improve their performance score by 1 or more.
3. Subject is pregnant, planning to become pregnant, or is lactating.
4. Subject has a history of empyema.
5. Subject has a history of chylothorax.
6. Subject has an uncorrected coagulopathy.

Randomization and Allocation

Randomization will be performed utilizing a computer system at Duke (the coordinating center) with permuted block randomization of random block length. Allocation will occur at the time of initial clinic visit following catheter insertion.

Data Collection

Data will be collected using paper clinical research forms at the clinical sites followed by direct entry into a web based, password protected REDCAP database. Duplicate databases will be stored on Duke and VA servers to safeguard data security.

Initial Data Collection

Data to be collected at the time of enrollment include age, sex, race, ethnicity, effusion side, type of malignancy, date of diagnosis, date of initial thoracentesis, Karnofsky performance score, ECOG performance score, comorbidities (anemia, asthma, cerebrovascular accident, chronic kidney disease, chronic obstructive pulmonary disease, coagulopathy, congestive heart failure, coronary artery disease, diabetes, deep vein thrombosis, pulmonary embolism, hypertension, hypothyroidism, hyperthyroidism, interstitial lung disease, nephrotic syndrome, peripheral vascular disease, cirrhosis of the liver), pleural fluid characteristics (pH, LDH, Protein, % lymphocytes, glucose, cytology results), prior chemotherapy, prior radiotherapy, prior immunomodulatory therapy, VAS dyspnea score, and SF-36 questionnaire. Data collected at randomization will be CXR score by treating and blinded physician.

Follow-up Data Collection

Karnofsky score, ECOG score, VAS dyspnea score, SF-36 questionnaire, and CXR scoring will be collected at the 30 day and 90 day clinic visits, or at the time of catheter removal. Thoracic ultrasound examination will be performed at time of catheter removal.

Subject Recruitment and Compensation

Consent Process- Consent form and material subject to IRB approval

Risk/benefit assessment- There are two primary risks to patients associated with this study. The first is the risk of respiratory failure associated with talc pleurodesis. Respiratory failure is a rare but well documented risk associated with the use of talc for pleurodesis. This event is rarely fatal and occurs roughly 1 in every 10,000 patients when utilizing graded talc. The second concern is obstruction of the tunneled pleural catheter by talc. This happens spontaneously in about 10% of patients and can be managed in >90% of these patients with the instillation of tissue plasminogen activator through the catheter. Previous trials of talc instillation through tunneled pleural catheters have not noted a higher than baseline rate of TPC blockage with this treatment regimen. Expected side effects of talc instillation include pain and fever which are temporary and can be treated with over the counter analgesics and anti-pyretics.

Potential benefits of participation in this study include less long-term fluid collection and potential earlier removal of the catheter.

Cost to the Subject- There will be no increased cost of care to the patients as the instillation will occur during routine follow up visit after TPC placement. Talc will be supplied as part of clinical care. Clinic visits are occurring as part of our routine clinical care for malignant pleural effusion treated with tunneled pleural catheters. Drainage bottles will be obtained through usual care pathways.

Data Analysis and Statistics

Power Calculation

Assuming a 45% rate of TPC removal in the control arm, and a 65% rate of TPC removal in the experimental arm (a 20% improvement) and a margin of error of 5% we calculate we would need to enroll 92 patients per group to have 90% power to detect a significant difference with $p<0.05$ using a one sided superiority test. Given a 10% dropout rate seen in the other two major studies within this field, we assume we would need 101 patient's per treatment arm. We anticipate including 2 centers in this study and we estimate that accrual will be reached within 36 months. Study will be completed at 40 months to allow for complete follow up of all patients enrolled.

[figure not shown]
Statistics will be performed by a statistician blinded to which treatment group allocation

Planned Interim Analysis

An interim analysis will be conducted once 100 subjects have been recruited and 90 day data collected. Analysis will be for the primary outcome only. Statistically significant difference in pleurodesis rates as measured by Fisher's Exact Test with $p < 0.05$ will trigger early termination of the study.

Data and Safety Monitoring

All study records will be kept securely by in the study coordinators or local site investigators office. Digital records will utilize secured Redcap database software on the Duke or VA networks. Only the study personnel will have access to the records. Subject data will be coded with a study number after recruitment. The code crosswalk key will be kept in a separate location from the study data.

References

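### No adverse-event review is scheduled between the day of talc and day 30 unless the catheter comes out earlier, and early observation covers one arm only, so temporary pain and fever are likely to be under-recorded and unevenly ascertained

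*Combined protocol and SAP*

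**What the plan says.** All references are to the combined protocol and SAP.

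- **Endpoint.** Design and Procedures lists "Secondary Endpoints: Quality-of-Life Assessment, dyspnea assessment, adverse events". It gives no definition, grading or analysis for adverse events.
- **Observation after talc.** Sclerosant Infusion Procedure: "The patients receiving talc will be monitored on-site for 2 hours for the development of dyspnea, followed by drainage of the catheter". It continues: "Vitals signs will be monitored for stability prior to discharge home". The Schedule of Events confirms that the 2-hour monitoring applies to the talc arm only.
- **Later review.** The Schedule places AE review at baseline (Day 0), day 30 and day 60. Follow up says: "Study subjects will return for clinic visits at day 30 and 90 after randomization, or a final visit at the time of catheter removal". Day 60 and day 90 disagree, but this does not affect the present point. Follow up also allows extra visits when clinically needed.
- **Telephone contact.** Inclusion criterion 5 asks patients to accept study requirements, "including follow-up visits and receiving study-related telephone calls". No call appears in the Schedule.
- **Expected talc effects.** Risk/benefit assessment: "Expected side effects of talc instillation include pain and fever which are temporary". It also names respiratory failure as one of two primary risks.
- **Anticipated events.** Adverse Events: "Anticipated adverse events include pain with drainage, catheter dislodgement, catheter malplacement, insertion site cellulitis, and empyema". That section adds lidocaine toxicity. Fever, pain from talc itself and respiratory failure do not appear there.
- **Diary.** Under Enrollment, every patient receives a drainage diary at randomization. Nothing says that it records symptoms.

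**The concern.** Talc is the only planned difference between the arms, and the protocol itself states which minor harms to expect from it. Those harms are described as temporary and treatable with over-the-counter drugs, so a patient who has them at home has little reason to call the clinic. With no scheduled review until day 30, many such episodes would be recorded only if the patient remembers and mentions them weeks later.

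The arms are also not observed alike. Talc patients are watched for 2 hours and controls are not. The visit at catheter removal depends on pleurodesis, the outcome talc is meant to change, so the recall interval may differ by arm as well.

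What is at stake is the tolerability comparison. It matters because the Background presents the combined strategy as workable for outpatients with no extra healthcare contact. The primary endpoint is not affected.

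**Working it through.** The plan states no figure to reproduce. The check sets the sections side by side, then illustrates the possible effect under labelled assumptions.

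**1. Opportunities to record an adverse event, by arm**

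| Time | Talc | Control |
|---|---|---|
| Day 0 | AE review, plus 2 hours for dyspnea and vital signs | AE review |
| After Day 0, before day 30 | Catheter-removal visit if it occurs; visits for clinical need; calls of unstated timing | Same |
| Day 30 | AE review | AE review |

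The Follow up and Follow-up Data Collection sections do not list adverse events among the items collected, so the Schedule row is the only source for the day-30 review. No section assigns AE review to the removal visit.

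**2. Who might be seen before day 30**

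The Power Calculation assumes removal rates of 65% (talc) and 45% (control). If these are read as removal by day 30, up to 65% and 45% could have a removal visit by then. The first scheduled contact would be day 30 for the remaining 100 − 65 = 35% and 100 − 45 = 55%. The waiting time therefore differs by arm on the plan's own assumptions.

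**3. Possible number of missed episodes (rates assumed)**

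Input from the Power Calculation: 101 talc patients. Assumed true rate of temporary pain or fever: 10% to 50%. Assumed capture by recall: 30% to 70%.

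- Affected: 101 × 0.10 = 10.1, to 101 × 0.50 = 50.5 patients.
- Recorded: 10.1 × 0.30 = about 3, to 50.5 × 0.70 = about 35 patients.

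**4. Effect on the difference between arms (rates assumed)**

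Reported difference = pT × cT − pC × cC, where p is the true rate and c the fraction captured. Assume pT = 20% and pC = 5%, a true difference of 15 points.

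- Equal loss of 25%: 15 × 0.75 = 11.25 points.
- Equal loss of 75%: 15 × 0.25 = 3.75 points.
- Unequal loss, with talc fully captured and control captured at 25%: 20 × 1 − 5 × 0.25 = 18.75 points, above the true 15.

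Equal loss shrinks the difference. Sufficiently better capture in the talc arm enlarges it. The documents do not say which applies.

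**5. Respiratory failure**

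At the stated rate of about 1 in 10,000, the chance of at least one case among 101 talc patients is 1 − (1 − 0.0001)^101 = 1.0%. If none occurred, the exact one-sided 95% upper bound would still be 1 − 0.05^(1/101) = 2.9%. Sample size, not visit timing, limits what the trial can say about this event.

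**The case against.** A reader might go further than the documents allow in five ways.

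- **That patients are unobserved from hour 2 to day 30.** They are not. Vital signs are checked before discharge, catheter removal brings a visit, and patients are to contact the team when drainage falls. Visits for clinical need are allowed, and a serious event would probably surface through one. The interval up to day 30 is a maximum. What remains is that none of these routes is a scheduled enquiry about mild symptoms.
- **That effects missing from the anticipated list will not be recorded.** The list is worded as non-exhaustive, the AE review is not confined to it, and pain appears in one form. The omission is an inconsistency with the Risk/benefit assessment, not an exclusion.
- **That the trial will understate talc's harm relative to control.** This is not shown. The trial is unblinded and the extra observation is in the talc arm, which tends to raise capture there, while recall loss tends to lower it. The net direction is open.
- **That respiratory failure will be missed.** It is not a minor event likely to be forgotten, and step 5 of the working shows that its limit is sample size.
- **That the safety of a particular dose is at issue.** The comparison is talc against no talc, and no doses are compared.

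Two further objections carry weight. The documents call pain and fever temporary but do not say when they begin. The diary page and case report forms are not reproduced, and the content of the calls is unstated, so symptom questions may exist somewhere. Both limit certainty. Neither supplies a scheduled, symmetric collection in the plan as written.

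**Conclusion.** The point holds in a limited form. Apart from an earlier catheter-removal visit or visits for clinical need, the only scheduled AE reviews around instillation are Day 0 and day 30, and the 2-hour observation is in one arm. Temporary pain and fever at home are therefore likely to be under-ascertained, and ascertainment differs by arm.

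The size and net direction of the between-arm bias cannot be computed, because the documents give no event rate and no capture rate. The ranges in the working are illustrations only. The conclusion assumes that some episodes begin or continue after discharge, and that the diary and calls do not already ask about them. It concerns a secondary endpoint and is worth acting on mainly because the remedy is so cheap.

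**What to change.** 1. Add daily lines to the drainage diary for pain, fever (yes/no) and analgesic or antipyretic use. Use the same page in both arms for a fixed period from randomization, for example 7 days, and keep the symptom lines going if the catheter is removed within that period. Tabulate the results by arm.
2. Reconcile the list in the Adverse Events section with the talc effects named under Risk/benefit assessment.
3. Optionally, use one of the telephone calls foreseen in inclusion criterion 5 as an early AE review in both arms, and enter it in the Schedule of Events.

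The first item costs a revised diary page and a little patient effort. The Schedule already has the diary reviewed at day 30, so no new visit or procedure is needed. The second is a wording change. The third costs one call per patient and sits less easily with the aim of avoiding extra healthcare contact, which is why it is optional. More minor events will be recorded. Self-report in an unblinded trial can still be influenced by knowledge of the allocation, and a common diary reduces the differences in timing and opportunity but not that influence.

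### The text lets a score taken at catheter removal replace later dyspnea and quality-of-life scores, against the fixed visits in the Schedule of Events; if followed, these secondary scores depend on the primary-endpoint event

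*Combined protocol and SAP*

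**What the plan says.** Three parts of the protocol text tie follow-up scores to catheter removal.

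- **Follow up:** "clinic visits at day 30 and 90 after randomization, or a final visit at the time of catheter removal (Figure 1". Dyspnea VAS and quality of life are taken at these times. Further visits are foreseen only on clinical grounds and carry no questionnaires.
- **Secondary Outcomes:** VAS and SF-36 at enrollment, day 30 and day 90, "or at the time of catheter removal if prior to the 30 day or 90 day clinical follow-up". The stated aim is: "The assessments will be examining stability of symptom control over the course of study enrollment".
- **Follow-up Data Collection:** performance scores, VAS, SF-36 and chest x-ray score "will be collected at the 30 day and 90 day clinic visits, or at the time of catheter removal".

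The **Schedule of Events** differs. The row "SOB VAS questionnaire", the SF-36 row and the adverse event (AE) review row are each marked at baseline, at 30 days and at the last column, "60 day follow-up visit". There is no removal column and no footnote ending assessments at removal.

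Under **Outcome Measures**, removal at 30 days is the primary endpoint. The pleurodesis definition given there includes "lack of respiratory symptoms of cough or shortness of breath previously attributed to pleural effusion".

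**The concern.** If sites follow the text, the event that the trial tests also decides when a patient is scored and whether a later score exists. The plan expects that event more often with talc, so the arms would be scored at different times in different proportions, and symptoms after removal would go unseen in more talc than control patients.

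The removal-day score is also selected. Under the primary outcome definition it is taken when effusion-related cough or dyspnea has just been judged absent. An aim of examining the stability of symptom control is poorly served if observation stops at that moment. The text of Data Analysis and Statistics gives no method for VAS or SF-36, so nothing there says how removal-day and fixed-day scores would be combined.

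**Working it through.** **Inputs.** Removal rates of 65% (talc) and 45% (control), and 92 per arm (101 with dropout), are from the Power Calculation. Deaths are ignored.

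**The plan's own figure.** The 92 does not reproduce from its stated inputs (45% vs 65%, one-sided 0.05, 90% power). With unpooled variance, n = (1.645 + 1.282)² × (0.45 × 0.55 + 0.65 × 0.35) / 0.20² = 101.7, so 102; with pooled variance it is 105. That is a separate matter. Here 92 serves only as a denominator.

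**Scores available if the text is followed**

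| | Talc | Control |
|---|---|---|
| Removed by day 30, no later score scheduled | 0.65 × 92 = 59.8 | 0.45 × 92 = 41.4 |
| Catheter still in, so a second fixed-day score is possible | 0.35 × 92 = 32.2 | 0.55 × 92 = 50.6 |

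The second row is a maximum, because removals after day 30 reduce it further. Under the schedule read literally, all 92 per arm are due at both visits, apart from death and dropout.

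**Timing of the first follow-up score.** Let m be the mean removal day among those removed by day 30 (assumed 10 to 25; not in the documents). The mean day of the first score is p × m + (1 − p) × 30.

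- m = 10: talc 6.5 + 10.5 = 17.0; control 4.5 + 16.5 = 21.0; gap 4.0 days.
- m = 25: talc 16.25 + 10.5 = 26.75; control 11.25 + 16.5 = 27.75; gap 1.0 day.

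This gap is small. The larger issue is what is missing after removal.

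**Can a direction be given?** Suppose removal-day scores stand in for second-visit scores. Let removed patients later worsen by d on average, and let a fraction f of those with a catheter at day 30 be removed before the second visit. Both are assumed equal in the two arms, and d has no source in the documents.

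- *Removal visit is final.* Shares with a stand-in score are 0.65 + 0.35f and 0.45 + 0.55f. The artificial difference is 0.20(1 − f)d in favour of talc: 0.20d at f = 0 and 0.10d at f = 0.5.
- *Removal-day score replaces only the next visit*, which the Secondary Outcomes wording allows. Only later removals have a stand-in: (0.35 − 0.55)f d = −0.20f d, in favour of control: 0 at f = 0 and 0.10d at f = 0.5.

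The sign therefore depends on which reading the sites adopt.

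**The case against.** **The conflict is partly one of omission.** The schedule never says in words that scores continue after removal. It also marks drainage diary review at both follow-up visits, although drainage ends at removal, so it may be only a summary that yields to the text. Figure 1 might settle the matter. All this weakens the table as evidence of intent. It does not help the text, which schedules no score after a *final* removal visit.

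**The text can be read as coherent.** If enrollment ends at removal, stability over enrollment has been examined. That is fair, but the length of observation is then set by the outcome and is expected to differ by arm.

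**Stronger readings that the documents do not support**

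- A reader might take "once 100 subjects have been recruited and 90 day data collected" as proof that questionnaires continue to day 90. That sentence governs an interim analysis restricted to the primary outcome.
- A reader might infer a serious loss of precision. Comparing only patients who still have a catheter multiplies the standard error by √[(1/32.2 + 1/50.6) / (2/92)] = 1.53. The plan never proposes that comparison; it treats the removal-day score as a planned assessment.
- A reader might assume that half of the remaining catheters come out before the second visit. That implies 45% + 0.5 × 55% = 72.5% removal in controls. The Background cites 48% by 12 weeks with daily drainage, which would put f near (0.48 − 0.45) / 0.55 = 0.055.
- A reader might infer that AE review stops at removal. The text sections on timing do not move AE review, and the table keeps it at the fixed visits. The doubt rests only on the word *final*.
- A reader might infer a bias favouring talc. As shown above, neither size nor direction follows from the documents.

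**Conclusion.** The point holds as a design weakness in the secondary endpoints. Three text sections let an assessment at removal take the place of later VAS and SF-36 scores, and the Schedule of Events shows fixed visits without that exception. If the text is followed, about 60 talc and 41 control patients of 92 per arm would have no score scheduled after removal by day 30.

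These counts rest on the plan's own removal rates, on the reading that the removal visit is final, and on ignoring deaths. The imbalance between arms arises only if talc changes the timing of removal, which is the trial's hypothesis. The primary endpoint is unaffected and no AE bias is claimed. The change is a cheap improvement, best made before data collection because scores not collected cannot be recovered.

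**What to change.** - State that VAS and SF-36 are collected from every randomised patient at day 30 and at the second follow-up, whether or not the catheter is out.
- Use the same questionnaire mode for all patients at each fixed day, for example self-completed by mail, or by telephone. Remote contact only for patients without a catheter would make mode depend on removal, and so on arm. Inclusion criterion 5 already foresees study telephone calls.
- Keep the removal-day score as an additional assessment. Compare arms at the fixed days, and report deaths and missing scores by arm at each day.
- State that AE review continues to the fixed visits, as the table shows.
- Reconcile the Schedule of Events (day 60) with Follow up, Secondary Outcomes and Follow-up Data Collection (day 90).

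**Cost.** Patients removed by day 30 need up to two extra contacts each: 2 × 92 × (0.65 + 0.45) = 202, or 2 × 101 × 1.10 = 222. Each later removal adds one: 0.90 × n × f, from about 5 (n = 92, f = 0.055) to about 45 (n = 101, f = 0.5). Patients who still have a catheter change mode but gain no assessment. Deaths lower these numbers. No new clinic visit or procedure is needed. The downsides are form burden for patients with a poor prognosis, and comparisons that remain among survivors.
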